14.14.3 Estimate Incremental Cost-Effectiveness Ratio

The primary ICER is estimated as the difference between mean costs of the modified TAU + TES group and the mean costs of the TAU group divided by the mean abstinence weeks of the modified TAU+TES group and the mean abstinence weeks of the TAU group. This ratio represents the additional cost of the experimental arm over TAU necessary to produce an additional drug-free week. We will estimate this ratio for both treatment costs and all medical costs. Similarly, a cost-effectiveness ratio will be estimated using QALYs in the denominator. We will estimate the cost-effectiveness ratios at 12 weeks and at 6 months. In total we will have

8 outcomes with the 4 outcomes using abstinence weeks as the denominator as the primary economic outcomes.

14.14.4 Power for Economic Hypothesis

We estimate the power for the outcome of cost for increased rate of abstinence at Week 12 given the target sample size of about 500 (about 250 participants per group). The primary effectiveness measure will be abstinent weeks. As above, we assume 2.4 weeks for TAU (SD=3.38) and 3.6 weeks for TAU+TES (SD=3.87). We use a standard deviation of 3.63. The additional costs over 12 weeks are assumed to be \$467 (SD=374) in the TAU group and \$823 (SD=659) in the intervention group. These numbers are derived from the TAU costs of the 12 week CM interventions for (1) cocaine abuse (2) and stimulant abuse. The expected CM payout is \$293 with 55% compliance assumed. The TAU+TES group also includes higher TAU treatment costs due to greater retention of 42% and a 20% reduction in TAU treatment costs from "reduced" TAU. The final parameter for estimating power in cost-effectiveness is the correlation between costs and effects. Because CM costs are highly likely to cost more for the most successful clients (greater payouts and greater treatment duration) there is a strong positive correlation. We assume a correlation coefficient of 0.15.

Using the equation for power for cost-effectiveness ratios (Glick et al., 2001), we find 96% power with a proposed sample size of 500. The study is powered at 90% for a cost effectiveness ratio of costs per abstinence week of \$920 per abstinence week.

Note on power for cost-effectiveness. A cost-effectiveness ratio is powered relative to its maximum acceptable value. The range of maximum acceptable values typically used is \$50,000 to \$100,000 per quality adjusted life year (QALY). However, clinical trials in the substance abuse research field generally have not used QALYs or even life years saved as a measure of effectiveness (as is often done in other areas of medicine). This is true for this project as well where the primary clinical outcome is a continuous drug free week. Recent data from a CTN study using QALYs found that for every 15 percentage point increase in the rate of abstinence (which converts to 1.8 weeks over 12 weeks), QALYs increased by 5 percentage points. We translate the \$50,000 per QALY threshold to \$1,400 per week of abstinence.

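### The $1,400-per-abstinent-week ceiling scales abstinence to 12 weeks but enters the QALY gain as a full 0.05 with no stated period, so the conversion and the economic power that depends on it are unsupported

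*Protocol*

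**What the plan says.** Section 14.14.4 (Power for Economic Hypothesis) explains that a cost-effectiveness ratio is powered against the largest value a decision-maker would accept, and gives the usual range as $50,000 to $100,000 per QALY. The primary ratio is in cost per abstinent week, so the section needs a conversion. It takes one from an unnamed CTN study: "every 15 percentage point increase in the rate of abstinence (which converts to 1.8 weeks over 12 weeks), QALYs increased by 5 percentage points". It then converts the $50,000 end of the range to a dollar figure of "1,400 per week of abstinence".

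The same section gives the planning inputs for costs and abstinent weeks, states 96% power with 500 participants, and states 90% power at $920 per abstinent week. It does not say which ceiling the 96% belongs to, and it gives neither alpha nor sidedness for the economic test.

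Section 14.14 makes cost per unit of abstinence time the primary ratio and cost per QALY the secondary one. Section 14.1.2 hypothesises that TAU+TES will be cost-effective.

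**The concern.** The two halves of the conversion are treated differently. The abstinence gain begins as a rate (15 percentage points) and is multiplied by 12 weeks. The QALY gain is also given in percentage points, but it is not multiplied by any period and is valued as 0.05 of a QALY. A QALY is a quality weight multiplied by time, so the number has no definite meaning until its period is known.

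$1,400 is the only acceptable value per abstinent week that the protocol derives for its primary economic ratio. If it is too high, the economic power looks better than it is. A reader of the results could also judge TES acceptable at a cost per abstinent week that does not meet the $50,000 per QALY standard it is meant to represent.

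**Working it through.** **Inputs, all from section 14.14.4.** Threshold $50,000 per QALY (range to $100,000). Abstinence gain 0.15 x 12 = 1.8 weeks. QALY gain 0.05, period not given. Abstinent weeks 2.4 and 3.6 (difference 1.2), common SD 3.63. Costs $467 (SD 374) and $823 (SD 659), difference $356. Cost-effect correlation 0.15. 250 per arm. Assumption: alpha 0.05 two-sided, with one-sided 0.05 also shown.

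**Step 1: reproduce the ceiling.** 50,000 x 0.05 / 1.8 = $1,389, which rounds to $1,400. This requires the 0.05 to be a complete 0.05 QALY set against 12 weeks of abstinence.

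**Step 2: what that requires if the QALYs accrue within the 12 weeks.**
- Mean utility difference between groups: 0.05 / (12/52) = 0.22.
- If all the benefit falls in the extra abstinent weeks: 0.05 / (1.8/52) = 1.44 per abstinent week, which is more than the distance from zero utility to full health.

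**Step 3: put both gains on the same T weeks.** Ceiling = 50,000 x 0.05 / (0.15 x T) = 16,667/T.
- T = 12: $1,389
- T = 24: $694
- T = 26: $641
- T = 52: $320

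Reading the 5 points as a quality weight and scaling it to 12 weeks gives the same as T = 52: 50,000 x 0.05 x (12/52) / 1.8 = $320. At $100,000 per QALY each ceiling doubles: $1,389 at 24 weeks, $1,282 at 26 weeks and $641 on the annual reading.

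**Step 4: power at each ceiling W.** Expected net benefit = 1.2W - 356. SE² = sum over the two arms of (W² x 3.63² + SDc² - 2 x W x 0.15 x 3.63 x SDc) / 250, where SDc is the arm's cost SD. Power = Phi(net benefit / SE - 1.96), with 1.645 in place of 1.96 for one-sided.

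| Ceiling W | Net benefit | SE | Ratio | Power, two-sided | Power, one-sided |
|---|---|---|---|---|---|
| $1,400 | $1,324 | $450 | 2.94 | 84% | 90% |
| $694 | $477 | $224 | 2.13 | 57% | 69% |
| $641 | $413 | $207 | 2.00 | 52% | 64% |
| $320 | $29 | $108 | 0.26 | 4.5% | 8.4% |

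Power falls so steeply because the planning ratio is 356 / 1.2 = $297 per abstinent week. A ceiling of $320 is barely above it.

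**Step 5: the starting point for the comparison.** At $1,400 the listed inputs give 84% two-sided or 90% one-sided, not the stated 96%. That is a separate discrepancy. The effect of the time base should be measured from the recomputed 84%.

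**The case against.** The strongest defence is that the period of the source study's QALY gain is unknown. If that study related QALYs over a longer follow-up to abstinence during a 12-week treatment phase, dividing 0.05 by 1.8 credits later benefit to treatment-phase abstinence, which can be legitimate. The section does not exclude this, but it does not say it either. So the defence stops anyone asserting a single corrected value. It does not support $1,400.

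Four stronger readings are tempting, and the protocol does not support them:

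- **That the right ceiling is $320 and the trial has almost no economic power.** The annual reading is the natural parallel to a rate of abstinence, but it remains an assumption. The result also depends on the $50,000 end of the range: the annual reading at $100,000 gives $641 and 52% power.
- **That $1,400 is impossible because a week of full health is worth only 50,000 / 52 = $962.** This holds only if all the benefit falls inside the abstinent week itself. Gains in other weeks, during or after treatment, are possible. A mean utility difference of 0.22 over 12 weeks looks large but is not impossible.
- **That $1,400 is a decision rule.** It appears only in a note on power, and nothing in sections 14.14 to 14.14.3 declares TES cost-effective at that value.
- **That the error takes power from 96% to 4.5%.** This merges the time-base problem with the separate failure of the 96% to reproduce.

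Two provisions also lessen the consequence. Section 14.14.5 plans to vary the ceiling ratio, and section 14.14.3 plans ratios with QALYs in the denominator, which need no conversion. Neither corrects the $1,400 itself.

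**Conclusion.** The point holds as a defect in the conversion. The $1,400 combines a gain scaled to 12 weeks with one whose period is missing, and the protocol gives no basis for combining them that way. At $50,000 per QALY, any matched period longer than 12 weeks lowers the ceiling. For the periods shown it lies between $320 and $694, about half to less than a quarter of the stated value, with two-sided power between 4.5% and 57% against 84% recomputed at $1,400.

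These figures assume matched periods, two-sided alpha of 0.05 and the section's own planning inputs. Which of them applies cannot be settled without the source period. The matter is confined to the secondary economic analysis: the co-primary endpoints are untouched, and section 14.4 bases the sample size of 500 on those endpoints alone.

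**What to change.** In section 14.14.4:

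1. State the period over which the 5-point QALY gain was measured in the source study.
2. Express abstinent weeks and QALYs over that same period, or say explicitly that QALYs gained after treatment are credited to 12-week abstinence and justify it.
3. Restate the ceiling per abstinent week for both $50,000 and $100,000 per QALY.
4. Restate economic power at each ceiling, naming the ceiling, alpha and sidedness beside each power figure.

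The cost is text and arithmetic only, with no change to data collection, sample size or the primary analyses. The likely price is a less favourable power statement for the economic hypothesis.

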14.14.5 Sensitivity Analysis

Sensitivity analyses will be performed to assess the sensitivity of our estimates of medical costs and cost-effectiveness to the assumptions made regarding some of the values that will be used in the analysis. We will consider how cost-effectiveness may change with: (1) different costs of TES; (2) different methods to handle attrition of cost data; and (2) different ceiling ratios.

14.14.6 Exploratory Economic

- (a) Costs related to criminal activity and contact with the criminal justice system. We will value each crime committed that has been reported on the NMS based on the sum of the value of victim costs and the risk of a homicide, and we will value charges and convictions for crimes based on criminal justice system costs (Rajikumar & French, 1997). We will assess differences in these costs using the techniques described 13.14.1(b).
- (b) Assessment of Fixed Costs of Program Start-up. In an additional economic analysis we will model the fixed costs incurred by the treatment programs as a result of the intervention which are primarily driven by training and other start up expenses. These costs are not part of the primary cost-effectiveness ratio for two critical reasons. First, they are setting dependent in that these costs on a per-patient basis, will depend largely on the skills of the staff and the size of the program. Second, these costs, as they are incurred during the clinical trial, may not reflect the costs

that would be incurred in a more generalized setting. However, because of the considerable cost constraints within CTPs, these fixed costs are critical. We will use this information to develop models which could demonstrate the financial consequences of adoption of a new therapeutic intervention at the program level.

15.0 DATA MANAGEMENT

15.1 Design and Development

This protocol will utilize a centralized Data and Statistics Center (DSC 2). The DSC 2 will be responsible for development of the electronic case report forms (eCRFs), development and validation of the clinical study database, ensuring data integrity, and training site and participating node staff on applicable data management procedures. A web-based distributed data entry model will be implemented. This system will be developed to ensure that guidelines and regulations surrounding the use of computerized systems used in clinical trials are upheld. The remainder of this section provides an overview of the data management plan associated with this protocol.

15.2 Data Collection Forms

The data collection process consists of direct data entry at the study sites into the EDC system(s) provided for the protocol. In the event that the EDC system(s) are not available, the DSC 2 will provide the sites with a final set of guided source documents and completion instructions. Data entry into the eCRFs should be completed according to the instructions provided and project specific training. The investigator is responsible for maintaining accurate, complete and up-to-date records, and for ensuring the completion of the eCRFs for each research participant. The DSC 2 is not responsible for maintaining any source documentation related to the study, including any films, tracings, computer discs or tapes.

15.3 Data Acquisition and Entry

Data entry into electronic CRFs (eCRFs) shall be performed by authorized individuals. Selected eCRFs may also require the investigator's written signature or electronic signature, as appropriate. Electronic CRFs will be monitored for completeness, accuracy, and attention to detail throughout the study.

15.4 Site Responsibilities

The data management responsibilities of each individual CTP will be specified by the DSC 2 and outlined in the DM plan.

15.5 Data Center Responsibilities

The DSC 2 will 1) develop a data management plan and will conduct data management activities in accordance with that plan, 2) provide final guided source documents and eCRFs for the collection of all data required by the study, 3) develop data dictionaries for each eCRF that will comprehensively define each data element, 4) conduct ongoing data monitoring activities on study data from all participating CTPs, 5) monitor any preliminary analysis data cleaning activities as needed, and 6) rigorously monitor final study data cleaning.

15.6 Data Editing

Completed data will be entered into the DSC 2 automated data acquisition and management system. If incomplete or inaccurate data are found, a data clarification request will be generated to the sites for a response. Sites will resolve data inconsistencies and errors and enter all corrections and changes into the DSC 2 automated data acquisition and management system in accordance with the data management plan.

15.7 Data Transfer

Data will be transmitted by the DSC 2 to the NIDA central data repository as requested by NIDA. The DSC 2 will conduct final data quality assurance checks and "lock" the study

database from further modification. The final analysis dataset will be returned to NIDA, as requested, for storage and archive.

15.8 Training

The training plan for CTP staff includes provisions for training on assessments, eCRF completion guidelines, data management procedures, and the use of computerized systems, as required.

15.9 Data QA

To address the issue of data entry quality, the DSC 2 will follow a standard data monitoring plan. An acceptable quality level prior to study lock or closeout will be established as a part of the data management plan. Data quality summaries will be made available during the course of the protocol.

APPENDIX A

Adverse Event Reporting Definitions and Procedures

Definitions of Adverse Events and Serious Adverse Events

Adverse Event: An adverse event (AE) is defined as any unfavorable and unintended sign including an abnormal laboratory finding, symptom or disease associated with the use of a clinical trial treatment or procedure, regardless of whether it is considered related to the clinical trial treatment or procedure, that occurs during the course of the study. Any new illness, symptom, sign or worsening of a pre-existing condition or abnormality is considered an AE. In order to avoid reporting pre-existing conditions as new AEs, and to assist in the assessment of a condition that has worsened in intensity or severity, a thorough medical history should be performed during the eligibility assessment phase to record any chronic, acute, or intermittent preexisting or current illnesses, diseases, symptoms, or laboratory signs. Stable chronic conditions, such as arthritis, which are present prior to clinical trial entry and do not worsen are not considered AEs. The AE case report form (CRF) is used to capture reportable AEs (as defined by the protocol) and may also be used to record follow-up information for unresolved events reported during previous visits. A study investigator is responsible for identifying and characterizing each AE, and is expected to follow appropriate reporting procedures.

Serious Adverse Event (SAE): A serious adverse event (SAE) is defined as any untoward medical occurrence that results in death, is life threatening, requires inpatient hospitalization or prolongation of existing hospitalization, results in persistent or significant disability/incapacity, or is a congenital anomaly/birth defect.

- Death: A death occurring during the study or which comes to the attention of the investigator during the protocol-defined follow-up after the completion of therapy, whether or not considered treatment-related, must be reported.
- Life threatening: Any adverse therapy experience that places the participant or participants, in the view of the investigator, at immediate risk of death from the reaction as it occurred (i.e., it does not include a reaction that had it occurred in a more serious form, might have caused death).
- In-patient hospitalization or prolongation of existing hospitalization
- Persistent or significant disability or incapacity
- Congenital anomaly/birth defect
- An event that required intervention in order to prevent one of the above outcomes

Laboratory Results

Laboratory results will be captured on laboratory collection CRFs. A study investigator is responsible for identifying and characterizing each abnormal lab result as clinically significant or not clinically significant and report any clinically significant lab results as AEs.

Eliciting and Monitoring Adverse Events: Qualified research staff will elicit participant reporting of AEs/SAEs at study assessment visits that have been designated to collect AEs and at any other time during the clinical trial that they have contact with or about the participant. Adverse event (medical and/or psychiatric) assessments will initiate once the participant is consented or randomized and will continue to occur through 30 days post last study visit. The research staff will obtain as much information as possible about the reportable AE/SAE to complete the AE/SAE forms and will consult with designated staff as warranted. Reportable SAEs will be reported as indicated below. A study investigator will review reportable AEs for seriousness, severity, and relatedness weekly. Appropriate site staff will review all reportable

AE documentation and verify accuracy of assessments at least once weekly when the participant attends the CTP to ensure that all of these AEs are appropriately reported and to identify any unreported AEs that require reporting. Reportable AEs/SAEs will be followed until resolution or stabilization or study end, and any serious and study-related AEs will be followed until resolution or stabilization even beyond the end of the study. Each participating site's Protocol PI is responsible for study oversight, including ensuring human research subject protection by designating appropriately qualified, trained research staff and medical clinicians to assess, report, and monitor adverse events.

Protocol monitors from the Clinical Coordinating Center (CCC) and local node staff will review the study sites and study data on a regular basis and will promptly advise sites to report any previously unreported safety issues and ensure that the reportable SAEs are being followed appropriately by the research staff. The node staff or CCC monitor will ensure that any unreported or unidentified reportable SAEs discovered during visits are promptly reported by the site to the Safety Monitor, NIDA, the Node or Protocol PI or designee, the lead investigator for the study and the IRB per local IRB requirements and will be reported on the monitoring report. Staff education, re-training or appropriate corrective action plan will be implemented at the participating site when unreported or unidentified reportable AEs or SAEs are discovered, to ensure future identification and timely reporting by the site. The NIDA CTN DSMB will also review data related to safety monitoring for this trial periodically at regularly scheduled meetings.

Assessment of Severity and Relatedness

Qualified research staff will review each reportable AE for seriousness, relatedness, and severity at each study assessment visit designated to collect AEs. The severity of the experience refers to the intensity of the event. The relatedness of the event refers to causality of the event to the study intervention. Relatedness requires an assessment of temporal relationships, underlying diseases or other causative factors and plausibility.

Severity: Severity grades are assigned by the study site to indicate the severity of adverse experiences. Adverse events severity grade definitions are provided below:

Grade 1	Mild	Transient or mild discomfort (< 48 hours), no or minimal medical intervention/therapy required, hospitalization not necessary (non-prescription or single-use prescription therapy may be employed to relieve symptoms, e.g., aspirin for simple headache, acetaminophen for post-surgical pain).
Grade 2	Moderate	Mild to moderate limitation in activity some assistance may be needed; no or minimal intervention/therapy required, hospitalization possible.
Grade 3	Severe	Marked limitation in activity, some assistance usually required; medical intervention/ therapy required, hospitalization possible.
Grade 4	Life- threatening	Extreme limitation in activity, significant assistance required; significant medical/ therapy intervention required, hospitalization or hospice care probable.
Grade 5	Death	

Relatedness: Relationship to therapy is defined as:

- Definitely related: An adverse event that follows a temporal sequence from administration of the test intervention and/or procedure; follows a known response pattern to the test intervention and/or procedure; and, when appropriate to the protocol, is confirmed by improvement after stopping the test intervention and cannot be reasonably explained by known characteristics of the participant's clinical state or by other therapies.
- Probably related: An adverse event that follows a reasonable temporal sequence from administration of the test intervention and/or procedure; follows a known response pattern to the test intervention and/or procedure and cannot be reasonably explained by the known characteristics of the participant's clinical state or other therapies.
- Possibly related: An adverse event that follows a reasonable temporal sequence from administration of the test intervention and/or procedure and follows a known response pattern to the test intervention and/or procedure, but could have been produced by the participant's clinical state or by other therapies.
- Unrelated: An adverse event that does not follow a reasonable temporal sequence after administration of the test intervention and/or procedure; and most likely is explained by the participant's clinical disease state or by other therapies.

Reporting and Management Procedures of AE/SAEs

Standard reporting, within 7 days of the site becoming aware of the event, is required for reportable AEs. Expedited reporting (within 24 hours of their occurrence and/or site's knowledge of the event) is required for reportable SAEs (including death and life-threatening events). A participating site must alert the NIDA-assigned Safety Monitor and the Lead Investigator of reportable SAEs within 24 hours of learning of the event. The SAE form and summary and any other relevant documentation should also be submitted with the initial report if adequate information is available at the time of the initial report to evaluate the event and provide a complete report. Local sites are responsible for reporting SAEs to their IRB, per their IRB's guidelines.

Additional information may need to be gathered to evaluate the SAE and to complete the AE and SAE forms. This process may include obtaining hospital discharge reports, physician records, autopsy records or any other type records or information necessary to provide a complete and clear picture of the SAE and events preceding and following the event. Within 14 days of learning of the event, an SAE form and related documents must be completed and entered into the data base. Documentation of the event that cannot be entered into the data base should be sent to the NIDA-assigned Safety Monitor. If the SAE is not resolved or stabilized at this time or if new information becomes available after the SAE form is submitted, follow-up SAE information must be submitted as soon as possible, but at least within 14 days after the site learns the information.

The study investigator at the site must apply his/her clinical judgment to determine whether or not an adverse event is of sufficient severity to require that the participant be removed from study intervention. The study investigator may consult with the Safety Monitor as needed. If necessary, an Investigator may suspend any trial treatments and institute the necessary medical therapy to protect a participant from any immediate danger. Subsequent review by the Medical Monitor, DSMB, ethics review committee or IRB, the sponsor, or relevant local regulatory authorities may also suspend further trial treatment at a site. The study sponsor and DSMB retain the authority to suspend additional enrollment and treatments for the entire study as applicable. A participant may also voluntarily withdraw from treatment due to what he/she perceives as an intolerable adverse event or for any other reason. If voluntary withdrawal is requested, the participant should be asked to continue (at least limited) scheduled evaluations, complete an end-of-study evaluation and be referred to appropriate care under medical supervision until the symptoms of any adverse event resolve or their condition becomes stable.

A NIDA-assigned Safety Monitor is responsible for reviewing all serious adverse event reports. The monitor will also report events to the sponsor and the Data and Safety Monitoring Board (DSMB). The DSMB will receive summary reports of all adverse events annually, at a minimum. Serious adverse events will be followed until resolved or considered stable, with reporting to the NIDA assigned Safety Monitor through the follow-up period. The site must actively seek information about the SAE as appropriate until the SAE is resolved or stabilized or until the participant is lost to follow-up and terminated from the study. The DSMB or the NIDA- assigned Safety Monitor may also request additional and updated information. Details regarding specific adverse events, their treatment and resolution, should be summarized by the Investigator in writing upon request for review by the NIDA-assigned Safety Monitor, DSMB, local ethics Committee/IRBs or regulatory authorities.
